- *Actigraphy.* Subjects will be asked to wear an individually configured actigraphy watch (Phillips Respiration Actiwatch 2) for the entirety of the study. This actiwatch collects data related to subject's sleep-wake cycle, including activity (via a built-in accelerometer) and light exposure (via a built-in luxometer). Watches are user friendly, requiring no user input to operate, and batteries last for ~6 weeks. Subjects will be reminded to keep clothing from covering up the luxometer on the actiwatch as much as possible.
- *Study diary.* Subjects will be asked to fill out a study diary, with daily entries for the entirety of the study. They will record when they went to bed, when they woke up, when they used the lightbox, and days they went to work. At this point subjects will be educated on principles of good sleep hygiene, such that all subjects start at the same baseline with respect to their understanding of good sleep hygiene principles. Study diaries will be coded via subject's ID with no other identifiable information listed.
- *Pain testing.* Pressure-pain threshold and tolerance will be quantified using a pressure algometer (AlgoMed Computerized Pain Pressure Algometer), a validated device used both experimentally and clinically with the pressure stimulus delivered to the thumbnail/thenar region of the non-dominant hand. Threshold will be determined by the amount of pressure that the subject perceives as mildly painful. Tolerance will be determined by the amount of pressure that causes the subject to withdraw their hand. This test takes ~20 min to complete.
- *Pain testing.* Cold Pressor Test. The cold pressor test may be used at VAPORHCS and at visits that are conducted remotely. This test will consist of an ice bath that subject's are instructed to submerge

their non-dominant hand into. Threshold and Tolerance will be measured with a stop watch. Threshold will be determined by the amount of time that the subject perceives the temperature as mildly painful. Tolerance will be determined by the amount of time that causes the subject to withdraw their hand. This will be done during a single trial. The upper limit of allowing the hand in the icebath is 5 minutes.

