- *Pain testing.* Ischemic Pain Test. Ischemic pain testing may be used at VAPORHCS and at visits that are conducted remotely. This test will consist of a manual blood pressure cuff that is placed on the subject's non-dominant upper arm and inflated to 300 mmHg. Threshold will be determined by the amount of time that the subject perceives the constriction as mildly painful. Tolerance will be determined by the amount of time that the subject allows the constriction to continue. This will be done during a single trial. The upper limit of allowing the hand the constriction is 5 minutes.
- *Department of Defense Head Trauma Events Checklist (DoD HTEC).* Determination of TBI status occur through a semi-structured diagnostic interview following the DoD HTEC guidelines. This interview will take ~15 min to complete.
- *Reimbursement.* Subjects will be compensated with up to \$20

Visit 3

- Visit 3 will occur ~4 weeks after Visit 2 and will take place within the VAPORHCS Sleep Disorders Clinic (building 100-6C), in Research Service (building 101, rooms 432A, 430, 404, and 533), remotely via phone/video conferencing, or at the subject's home.
- *Measures.* The same series of questionnaires and pain testing conducted at Visit 1 will be repeated.
- *Equipment.* Subjects will return all equipment, including the actiwatch, lightbox and/or sham device.
- *Reimbursement.* Subjects will be compensated with up to \$60

Visit 4

- Visit 4 will occur ~4 weeks after Visit 3 and will take place within the VAPORHCS Sleep Disorders Clinic (building 100-6C), in Research Service (building 101, rooms 432A, 430, 404, and 533), remotely via phone/video conferencing, or at the subject's home.
- *Measures.* The same series of questionnaires and pain testing conducted at Visit 1 will be repeated.
- *Reimbursement.* Subjects will be compensated with up to \$20
- *End of study debrief.* Subjects will be debriefed about our experimental design, given the inclusion of a placebo-controlled condition. We will provide subjects with a written description that we will describe to them in person and address any questions they may have.

Mailed forms and equipment. In an effort to reduce subject's time at the Portland VA we may mail consent forms, questionnaires, equipment and pre-addressed, pre-paid return envelopes directly to their homes. Instructions will be provided via phone or video conferencing.

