- **Morning Bright Light Therapy:** Light from a lightbox is essentially indistinguishable from natural light from the sun and consists of broad-spectrum white light. Morning bright light from a lightbox poses very minimal and rare risks. One study showed that light intensity of 10,000 lux received for an average of 40+ min per day over a five-year period had no major side effects. Minimal and uncommon side effects included eye irritation, irritability, headache, nausea, sensation of glare, dryness of eyes, and dryness of skin (as can occur from natural sunlight exposure). A rare occurrence of mania or rapid-cycling may occur in those with Bipolar Disorder due to too much exposure to bright light. For this reason, this study will exclude those with Bipolar Disorder. The manufacturer notes in the user guide that people with macular degeneration may be more at risk of retinal damage from blue light and should avoid it. Although the lightbox emits very little blue light, those with macular degeneration will be excluded from the study, as stated above in *Inclusion and Exclusion Criteria*. If problems are experienced, participants are free to stop the study at any time and/or call the Study Coordinator with any questions or issues.
- **Negative ion generator:** The negative ion generator will be modified so that it does not emit negative ions, so there will be no side effects from negative ions.
- **Actiwatch:** Participants may experience skin irritation from the actigraphy watch wristband, although very uncommon. Participants will be told to remove the actigraphy watch if this occurs. This would not exclude subjects from further participation.
- **Pressure algometer pain testing:** Pressure algometry has minimal risk for discomfort. Some studies, like this one, have the potential to cause "peripheral nerve stimulation." Peripheral nerve stimulation is a light touching sensation on the skin surface, lasting only for a few seconds. It may cause mild discomfort but is not harmful. There is a possibility that participants may experience some temporary redness or report some tenderness after the test. If at any point a participant expresses more than mild discomfort and/or wants to stop the test, we will stop.
- **Cold pressor pain testing.** The cold pressor test has minimal risk for discomfort. There is a possibility that participants may have some temporary redness or sensitivity after the test. If at any point a

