participant expresses more than mild discomfort and/or wants to stop the test, they will be instructed to remove their hand from the ice bath. We will not allow the research subject to have their hand submerged for more than 5 minutes to prevent any tissue damage.

- Ischemic pain testing. The ischemic pain test has minimal risk for discomfort. There is a possibility that participants may have some temporary numbness or sensitivity after the test. If at any point a participant expresses more than mild discomfort and/or wants to stop the test, their blood pressure cuff will be immediately deflated.

Other.

- Because this study collects protected health information, there is always a risk of a breach of confidentiality. This risk is addressed below under *Privacy and Confidentiality*.

The possible benefits to the participants and to future understanding and improvements in delivery of sleep-related care to Veterans are reasonable and outweigh the risks of minor and rare physical harm, emotional distress, or breach of confidentiality to study participants.

Participant Safeguards:

This study will not include any vulnerable populations. Potential participants will be gauged for their interest in the study prior to being provided a consent form. Those participants that can verbally acknowledge understanding of the study and agree to participate will be consented by trained study personnel. If it appears that the subject is experiencing decisional impairment or an inability to understand the study, such as failing to repeat back the basic concepts of the study, that person will not be permitted to participate.

Suicidality:

In the event that a participant expresses the thought of harming themselves when they are at the clinic for the overnight sleep test, the sleep lab technician or the researcher, if present, will accompany them to the Emergency Department for a warm-transfer.

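### The pain-test stop rule can end a test before tolerance is reached, so recorded tolerance would mix true withdrawals with staff-imposed stops

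*Protocol*

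**What the plan says.** The Visit 2 part of Research Design and Methods takes two measures from each pain test.

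- **Pressure algometer.** For the first measure the text reads "Threshold will be determined by the amount of pressure that the subject perceives as mildly painful". For the second measure it reads "Tolerance will be determined by the amount of pressure that causes the subject to withdraw their hand".
- **Cold pressor.** For the first measure the text reads "Threshold will be determined by the amount of time that the subject perceives the temperature as mildly painful". For the second measure it reads "Tolerance will be determined by the amount of time that causes the subject to withdraw their hand". The test is a single trial with a cap of 5 minutes.
- **Ischemic test.** Threshold is the time at which the constriction is felt as mildly painful. For the second measure the text reads "Tolerance will be determined by the amount of time that the subject allows the constriction to continue". Here too there is one trial, capped at 5 minutes.

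Risks and Side Effects, under Physical, gives a stop rule for each test.

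- **Pressure algometer.** "If at any point a participant expresses more than mild discomfort and/or wants to stop the test, we will stop".
- **Cold pressor.** The rule applies throughout the test and reads "participant expresses more than mild discomfort and/or wants to stop the test, they will be instructed to remove their hand from the ice bath".
- **Ischemic test.** The rule again applies throughout and reads "participant expresses more than mild discomfort and/or wants to stop the test, their blood pressure cuff will be immediately deflated".

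The study timeline schedules pain assessment at Visits 2, 3 and 4. The Aim 2 hypothesis names self-reported pain and pressure algometry. The cold pressor and ischemic tests are described as ones that may be used.

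**The concern.** Tolerance can be observed only if the stimulus continues past mild pain until the participant ends it. The stop rule tells staff to end the stimulus once the participant expresses anything stronger than mild discomfort. Both instructions govern the same test, and they name different end events.

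What is at stake is the meaning of the tolerance value. A value recorded at a staff stop shows only that the participant had tolerated the stimulus up to that point. If it is entered as tolerance, it understates the quantity that the Visit 2 section defines. A change between visits could then reflect how readily the participant spoke up, or how the tester applied the rule, as well as any change in pain tolerance.

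**Working it through.** No figure in the plan bears on this point, so the check compares the two sections and follows the order of events.

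**1. Order of events.** Within one test, threshold comes at mild pain. The stop trigger comes at any expression of more than mild discomfort. Tolerance comes at withdrawal, or when the participant no longer allows the stimulus. Pain and discomfort can be placed on one scale here, because the scientific rationale itself defines the pressure pain threshold by the onset of either one. The trigger therefore falls after threshold and can fall before tolerance.

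**2. The two limbs of the rule.** Wanting to stop is compatible with tolerance, because it is in substance the tolerance event. Expressing more than mild discomfort is a separate condition and, joined by and/or, is sufficient alone. The action that follows is staff-led for all three tests: staff stop the algometer, instruct removal of the hand, or deflate the cuff. The conflict comes from this limb only.

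**3. What is recorded.** For one participant at one visit, let T be the pressure or time at which the participant would withdraw. Let S be the pressure or time at which more than mild discomfort is first voiced, with S infinite for a participant who stays silent. If the rule is followed, the recorded value Y is:

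- Algometer: Y = min(T, S)
- Cold pressor and ischemic test: Y = min(T, S, 5 minutes)

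If S is not below T and no cap intervenes, Y = T and tolerance is observed as defined. If S is below T, Y falls short of T and is a lower bound.

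**4. Consequence for comparisons.** Leaving the cap aside, Y = T − max(T − S, 0). The difference in mean Y between arms equals the difference in mean T minus the difference in mean shortfall, max(T − S, 0). The shortfall cancels only if its mean is the same in both arms. The same identity holds for change between visits.

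**5. Extent.** The target is 100 participants with pain assessment at three visits, so at most 100 × 3 = 300 participant-visits are exposed. The share with S below T depends on how many participants speak before withdrawing. The document gives no information on this, so the share could lie anywhere from none to all.

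**6. Exemption or recording rule.** No part of the protocol exempts the tolerance phase from the stop rule, and none says how to record a test that the rule ends before withdrawal.

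**The case against.** The strongest case on the other side has four parts.

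**The trigger is an expression.** The rule responds to what a participant says or shows. Someone who reports threshold and is then silent until withdrawal gives a valid tolerance with the rule followed to the letter. This stands. A reader might infer that tolerance cannot be measured at all, that every test ends just above threshold, or that the range between the two shrinks to nothing. The text supports none of these.

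**The sections can be read together.** The stop wording sits in a participant-protection section, one limb matches the tolerance event, and withdrawing the hand is itself a way of expressing discomfort. This stands in part. It does not explain the other limb, which acts alone and directs staff to end the test. The same section also describes the physical discomfort from pain testing as mild, which fits a limit on intensity better than a bare right to withdraw.

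**The outcome carries limited weight.** Aim 2 names self-reported pain and pressure algometry. It does not name tolerance, and the other two tests are optional. Self-reported pain and all threshold measures are untouched. This stands and limits the importance of the point.

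**Uneven application is conjecture.** The protocol says that data-collection staff will be trained, and the test script and data form are not shown, so a stop reason may be recorded there. This also stands. A reader might infer tester-dependent results or a bias between arms. The document shows neither, and the same rule applies to both arms. Even so, training cannot settle which of two conflicting instructions to follow, and an analysis plan cannot recover a stop reason that was never collected.

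**Conclusion.** The tolerance definitions and the stop rule conflict for all three pain tests. If the rule is followed, participants who voice more than mild discomfort before withdrawing contribute a lower bound, and those who do not contribute true tolerance. Unless the reason for ending is recorded, the two kinds of value cannot be separated.

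The effect is confined to tolerance, and its size cannot be computed from the document. The conclusion assumes that staff follow the stop rule as written and that at least some participants speak before withdrawing. Neither assumption is tested in the protocol. The second is plausible in people enrolled for moderate to severe pain, who must signal threshold while the cold pressor or ischemic stimulus continues. The 5-minute caps also limit tolerance in those two tests, but they are stated openly and are not part of the contradiction.

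The point should be corrected because the two instructions disagree as written and the repair is cheap. It does not show that the pain outcomes as a whole are lost.

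**What to change.** 1. Reconcile the Visit 2 pain-testing text with Risks and Side Effects, separately for each test, so that the stop rule and the tolerance definition are compatible. Which rule stands is for the investigator and the IRB.
2. Record why each test ended: participant withdrawal, staff stop or, for the cold pressor and ischemic tests only, the 5-minute cap.
3. If the stop rule stays as written, analyse staff-stopped and capped values as right-censored and not as observed tolerance. Standard censored-data methods assume that censoring is unrelated to the unseen value. That is doubtful for staff stops, because voicing discomfort is likely to go with lower tolerance. Report the number of staff stops by arm and visit, and check how far the result depends on that assumption.

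The cost is protocol and test-script wording and one extra field on the pain-test form. No visit, test or sample-size change is needed. For tests already done, the stop reason can be used only if it was noted at the time.

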- Participants will be asked to fill out demographics information which will include their name (including name at birth), date of birth, city/town of birth, email and physical address, phone number, health history, and military history.
- Individuals without a medical record at the VA will be asked permission for study staff to request their medical record pertaining to sleep and traumatic brain injury.

Visit 2

- Visit 2 will occur ~2 weeks after visit 1. It can take place within the VAPORHCS Sleep Disorders Clinic (building 100-6C), in Research Service (building 101, rooms 432A, 430, 404, and 533), remotely via phone/video conferencing, or at the subject's home.
- *Questionnaires.* Subjects will complete baseline questionnaires. They take ~30 min to complete and include past medical history and self-reported measures on sleep, social habits, quality of life, mental health, pain, and other metrics related to subject's prior trauma exposure history. All questionnaires are validated and will be completed via pen and paper. Medical history and testing related to sleep will be accessed from the participants' VA medical records by study staff with VA credentials. Subjects may elect to complete these questionnaires at either this or subsequent visits as needed. Questionnaires may be mailed if completed remotely.
- *Equipment.* Subjects will be randomized to receive a lightbox (LightPad mini, Aurora Light Solutions) or sham-control modified negative ion generator. Devices will be modified by completely disconnecting the electrical wiring required for negative ion generation. This will be verified using a voltmeter. A small fan may be installed to emit a low humming noise as an indicator of activity. They will be instructed to use either device for 60 min every morning after waking up starting 2 weeks following this visit and continuing for 4 weeks. Light sensitive devices, called HOBOs, will be attached to the lightboxes which will track when the lightbox is turned on or off, as a secondary measure of light delivery.

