Video Conferencing. If the subject is comfortable and equipped, we may conduct visits using video conferencing, such as VA Video Connect or other VA approved methods (skype, facetime, google hangouts, etc.). A link to the video chat will be emailed participants via Azure RMS encrypted email. For VA Video Connect (VVC), this email is entered into the VCC platform and an email is automatically generated.

At home visits. In special circumstances study personnel may travel to the subject's homes in order to conduct the visit more comfortably. Equipment, data, and specimens will travel in between the home and the VA only.

Phone calls. In between visits subjects will be contacted up to 2 times per week as needed. They will be assessed for understanding and compliance and given the opportunity to asked questions. Questions will be asked about their sleep, pain, and quality of life metrics.

Emails. Communication via RMS Azure encrypted email may be established between the subject and study coordinator in order to allow subjects to freely ask any questions they may have.

Study Population:

Number of subjects. The target population will consist of n=100 subjects. In order to meet this enrollment target we anticipate that up to 400 individuals may need to be recruited (consented) and screened.

Eligibility Criteria. Only Veterans and non-Veterans who are physically and mentally able to provide written and verbal informed consent and have a medical record-confirmed or physician confirmed diagnosis of TBI, will be included in this study. Additional criteria are as follows:

- 1) Current self-reported sleep-wake disturbances (defined by clinically abnormal Insomnia Severity Index and/or Functional Outcomes of Sleep scores)
- 2) Moderate to severe pain (defined as a score of ≥ 4 on an 11-point scale⁹⁰) persisting for longer than 6 months
- 3) Do not have a diagnosis for dementia
- 4) Are not currently using a lightbox or negative ion generator
- 5) Are not night-shift workers
- 6) Are English speaking with phone access
- 7) Are 18 years of age or older
- 8) Do not have macular degeneration or bipolar disorder (both are relative contraindications to regular bright light exposure)
- 9) No suicidal ideation
- 10) No cancer diagnosis in the past 6 months
- 11) At least 6-12 months of being surgery free
- 12) No evidence of drug and alcohol dependency (defined by the substance abuse and dependency scale).
- 13) Are currently living within the United States.

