- **Mail-** (*This option will be used in cases where DocuSign is not feasible for any reason.*) Study staff will mail the consent form and HIPAA authorization form for the participant to review and then set up a meeting for study personnel to talk through the forms with the potential participant. Study personnel will go through each section of the consent form and HIPAA authorization form and address any questions the potential participant may have. If the subject agrees, they will be instructed to sign and date the forms and return them with the prepaid, pre-addressed envelopes provided. When the study team receives these forms, they will also sign and mail back the signed copy of the forms.

Risks and Side Effects:

The delivery of usual care is never altered by this study. Study risks include breach of confidentiality, psychological discomfort in completing study questionnaires, and mild physical discomfort from MBLT, and pain testing.

Psychological.

- **Questionnaires and Neuropsychological testing:** There is a small risk that completing questionnaires could be stressful, discomforting, or mildly embarrassing to the participants. The questionnaires take approximately ~30 min to complete. Since questions are asked about mood, including thoughts of self-harm and depression, there is a possibility that information about thoughts of suicide or evidence of depression will be gained that will require an intervention. How this information will be handled is discussed below in the *Suicidality* section.

Physical.

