If during a follow-up phone call after the sleep test the volunteer expresses thoughts of harming themselves, then the researcher will contact the VA national crisis line at [contact] or [name] or the local suicide prevention line at [name] and connect the individual to that help by phone. In the event a direct phone transfer cannot be completed, then the researcher will ask that the participant remain available by phone. The researcher will provide the VA National Suicide Prevention Hotline with the name and phone of the participant and the VA Hotline will then phone the participant. The researcher will follow-up afterwards by phone to ensure that the participant has received adequate help and is safe.

In the event that questionnaire answers indicate depression or suicidality, their primary mental health provider will be notified. If they do not have a mental health provider, then their primary care physician will be notified to make a referral. If there is an immediate suicidal ideation, we will walk the participant to the emergency room for a warm transfer.

Benefits:

Participants may directly benefit from this study through the designated morning bright light. Outcomes include improved quality of sleep, an increase in quality of life, improved cognition, and reduction of pain. Subjects will receive modest monetary compensation for their time (see *Subject Compensation*).

Protected Health Information:

The following protected health information (PHI) will be collected in this study: full name, phone number, dates of research visits, date of birth, full mailing address, email address, and last four digits of the social security number. Demographics such as identified race & ethnicity will be collected and history regarding diagnosis of a sleep disorder; medical history will be confirmed or examined in chart and information regarding TBI, PTSD, and/or depression may also be collected. Information regarding drug and alcohol dependency will be examined for the purpose of determining eligibility to participate in the study and research personnel

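### Two of the three suicidality branches are triggered by a sleep test this trial does not perform, and the only immediate protective step for ideation found on a questionnaire cannot be carried out remotely

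*Protocol*

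**What the plan says.** The Suicidality section has three branches.

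- **On-site.** It applies if a participant "expresses the thought of harming themselves when they are at the clinic for the overnight sleep test". An escort to the Emergency Department follows, by a sleep lab technician or by a researcher who is on hand.
- **Phone.** "If during a follow-up phone call after the sleep test the volunteer expresses thoughts of harming themselves", the researcher connects the participant to a crisis line. If a direct transfer fails, the hotline is given the participant's details and calls back. The researcher follows up by phone afterwards.
- **Questionnaire answers.** If answers indicate depression or suicidality, the mental health provider is notified, or the primary care physician if there is none. The section then adds: "If there is an immediate suicidal ideation, we will walk the participant to the emergency room for a warm transfer".

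Two other sections depend on this one. Risks and Side Effects (Psychological) says that "there is a possibility that information about thoughts of suicide or evidence of depression will be gained that will require an intervention" and refers the reader to Suicidality. Participant Safety, in the Data and Safety Monitoring Plan, provides for referral when questionnaire data show depression or suicide risk, giving item 9 of the PHQ-9 as its example. For indicated thoughts of self-harm it points back to Suicidality.

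On how contacts take place, Visits 2, 3 and 4 may each be held at the site or "remotely via phone/video conferencing, or at the subject's home". The Visit 2 text adds: "Questionnaires may be mailed if completed remotely". The Video Conferencing paragraph says "we may conduct visits using video conferencing, such as VA Video Connect or other VA approved methods". Phone Calls allows contact up to twice a week between visits.

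**The concern.** The stated triggers do not match the contacts this trial makes. Staff must infer that wording about a sleep test is meant for ordinary study visits and the between-visit calls. For immediate ideation found on a form completed away from the site, the urgent step the protocol prescribes is physically impossible, and the route that would work is worded for a different situation.

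What is at stake is participant safety, not inference. The protocol expects such disclosures, because it asks about mood and self-harm and says that an intervention may be needed. Instructions for an urgent event should be usable as written.

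**Working it through.** No arithmetic beyond counting applies, so the check sets the Suicidality section beside the rest of the protocol.

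**Step 1: is there a sleep test in this trial?**

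- Study Overview and Timeline lists 6 procedure rows: informed consent, actiwatch, pain assessment, lightbox or sham, questionnaires and daily device use. Sleep tests: 0 of 6.
- The descriptions of Visits 2 to 4 measure sleep by questionnaire, actigraphy and diary. On earlier testing, Visit 2 says "Medical history and testing related to sleep will be accessed from the" VA medical records of participants, so such results are read from the chart and not produced by the study.
- The physical risks listed cover the lightbox, the ion generator, the actiwatch and the three pain tests. None concerns a sleep test.
- Step-by-Step Guidance has 7 numbered steps. Sleep tests: 0 of 7.

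**Step 2: how many branches rest on it?** The on-site and phone branches do and the questionnaire branch does not, so 2 of 3. The on-site branch also names a sleep lab technician, who has no role in any visit description.

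**Step 3: which actions work for a questionnaire showing immediate ideation?**

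| Action | Where stated | Form completed on site | Form completed remotely or mailed |
|---|---|---|---|
| Notify mental health provider or primary care physician | Suicidality | yes | yes |
| Refer for follow-up | Participant Safety | yes | yes |
| Walk to the emergency room | Suicidality | yes | no |
| Crisis-line transfer, call-back and follow-up | Suicidality, phone branch | not stated for this case | workable, but not stated for this case |

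The first two actions do not depend on location, but neither is an immediate hands-on response. The third is, and it fails off site. At a home visit staff may be present, but a walk to the emergency room is still not a realistic instruction. The fourth is worded for thoughts voiced on a call after the sleep test, not for answers on a form.

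**Step 4: how many visits are exposed?** Questionnaires are scheduled at Visits 2, 3 and 4, which is 3 of 4 visits. All 3 may be held by phone or video or at the participant's home. Eligibility Criteria requires only residence in the United States, so a remote participant may be far from the site.

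**Step 5: does another section repair this?** Participant Safety and Risks and Side Effects send self-harm disclosures to the Suicidality section with no sleep-test condition. That helps with the triggers. Neither adds an immediate step for remotely completed questionnaires.

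**The case against.** The strongest reply is that the protocol, read as a whole, already contains the necessary routes. Participant Safety says without condition that the Suicidality steps follow when a participant indicates thoughts of self-harm, so the sleep-test phrases are stale wording that no sensible researcher would treat as a bar. A researcher who hears such thoughts on a study call would use the crisis line, and one who is present at a clinic visit would escort the participant. Provider notification and referral apply regardless of location. People with suicidal ideation are excluded at entry, and participants stay under usual care for their sleep complaint. Operational documents that are not shown, such as the phone scripts, the questionnaire packet and the procedure for handling questionnaire data, may cover remote cases.

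Much of this stands, and it rules out two stronger readings. A reader might infer that remote participants have no response at all, or that the walk is the only action for questionnaire-detected suicidality. The text does not support that, because notification and referral apply to them too. A reader might also infer that the escort and the crisis line are unavailable in this trial because no sleep test takes place. The unconditional cross-references argue against that.

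Two things remain. Inference about intent does not supply a step that is not written, and none is written for immediate ideation on a form completed off site. The entry criterion lowers the expected frequency, but the protocol itself plans for such answers during the study. The unseen documents cannot be assessed, and the two safety sections point to Suicidality for self-harm, not to scripts.

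**Conclusion.** Wrong as written, and it should be fixed. Two of the three branches carry a trigger that cannot occur in this trial. One prescribed urgent action cannot be carried out in a setting the protocol allows for all 3 questionnaire visits.

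The practical size is unknown, because the protocol gives neither the share of remote visits nor the number of mailed questionnaires. Partial safeguards exist, so this is a gap in the immediate response and not an absence of any response. The conclusion concerns the protocol text only and assumes that staff cannot walk a participant to an emergency room from a remote or home contact. It has no bearing on sample size or analysis.

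**What to change.** In the Suicidality section:

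1. Replace the on-site trigger with *at any on-site study visit* and delete the sleep lab technician.
2. Replace the phone trigger with *any phone or video study contact*.
3. Limit the walk to the emergency room to on-site visits.
4. Apply the existing crisis-line route (transfer, call-back and follow-up) to immediate ideation found at remote or home contacts or on returned questionnaires. Keep provider notification and referral as they are.

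An emergency-services step and a set time for reviewing mailed forms are optional additions for the investigator and the IRB to consider.

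The cost is protocol wording and IRB review. The routes already exist in the section, and design, sample size and analysis are unaffected.
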